- 6. Change in additional inflammatory markers from baseline to Week 12:
 - a. IL-10
 - b. TGF-β
- 7. Assessment of change in homeostatic model assessment for insulin resistance (HOMA-IR) from baseline to Week 12

Whole Biome Study No: WB01-202_Ver 2_Amend 3 06/19/18

Page 7 of 45

(https://www.dtu.ox.ac.uk/homacalculator/)

- 8. Assessment of change in the Matsuda index from baseline to Week 12 [Formula for Matsuda index: ISI(comp) = $10,000 / \sqrt{[(G_0 \times I_0)(G_{mean} \times I_{mean})]}$, where
 - G_0 Fasting plasma glucose concentration (mg/dl)
 - I_0 Fasting plasma insulin concentration (mIU/l)
 - G_{mean} Mean plasma glucose concentration during OGTT (mg/dl)
 - OGGT oral glucose tolerance test
 - I_{mean} Mean plasma insulin concentration during OGTT (mU/l)
 - 10,000– Simplifying constant to get numbers from 0 to 12
 - $\sqrt{-}$ Correction of the nonlinear values distribution
- 9. Assessment of change in fasting lipid panel [total cholesterol, LDL cholesterol, HDL cholesterol, and triglycerides (TGs)] from baseline to Weeks 4, 12, and 16
- 10. Change in body weight from baseline to Weeks 2, 4, 12, and 16
- 11. Change in BMI from baseline to Weeks 2, 4, 12, and 16
- 12. Change in waist circumference between baseline and Week 12
- 13. Change in fecal microbiome from baseline to Weeks 4, 12, and 16
- 14. Change in responses to Hospital Anxiety and Depression Scale (HADS) questionnaire from baseline to Week 12
- 15. Change in response to FACIT D&AD and Victoria Bowel Performance Scale Questionnaire

Following completion of the Week 12 visit, subjects will discontinue study product. They will then return to the clinic for a final visit at the end of Week 16, bringing with them a frozen stool sample collected during the prior 3 days to assess the persistence of the administered microorganisms in stool ~4 weeks after discontinuing ingestion. In addition, fasting glucose, insulin, and lipid panel will be collected at Week 16 to evaluate the persistence of changes in these parameters.

E. Study Product Portion Selection:

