Selection of study product portion size was guided by the exposure in Sprague-Dawley rats for 28 days and a human safety study as described above under Study Product Safety. In the human safety study, subjects consumed 7.0×10^9 CFU of strain WB-STR-0005, 4.0×10^9 CFU of strain WB-STR-0006, and 2.0×10^8 CFU of strain EXT-STR-0001 daily for 7 days, followed by a 5-fold increase in consumption to 3.5×10^{10} CFU of strain WB-STR-0005, 2.0×10^{10} CFU of strain WB-STR-0006, and 1.0×10^9 CFU of strain EXT-STR-0001 daily for an additional 7 days. The administered strains were detected in stool by the end of the first week of consumption, with an

Whole Biome Study No: WB01-202_Ver 2_Amend 3 06/19/18

Page 8 of 45

increase in quantity following the 5-fold increase in consumption.

F. Study Structure:

This is a balanced, parallel-arm, double-blind, placebo-controlled study consisting of an initial screening visit, a randomization visit on Day 0, and subsequent visits at Weeks 2, 4, 8, 12, and 16. In addition, phone visits will be conducted at Weeks 6 and 10 to ensure timely capture of adverse events and promote compliance.

Table 1: Daily Microbial Ingestion in Study Product

Tubic II Dully	Mici obiai iligo	coulon in otaay	Troudet		
Intervention	WB-STR-0006	WB-STR-0005	EXT-STR-0001	WB-STR-0001	WB-STR-0008
	(CFU/day)	(CFU/day)	(CFU/day)	(CFU/day)	(CFU/day)
Placebo	Colloidal silico	on dioxide, a noi	n-active GRAS i	ngredient.	
(WBF-0009)					
WBF-0010	3.3×10^9	1.6×10^{10}	2.0×10^9	None	None
WBF-0011	3.3 x 10 ⁹	1.6×10^{10}	2.0×10^9	1.2 x 10 ⁹	9.0×10^8

The screening visit to qualify for participation will happen between Day -7 and Day -14. Randomization will happen at the Day 0/Baseline visit along with the initiation of the randomly assigned study product twice daily, 3 capsules taken within 30 minutes before each morning and evening meal. Administration of study product will cease at the time of the 12-week visit as the subjects enter a 4-week wash-out period. At the final visit at the end of Week 16, the subjects will be asked to bring 1 frozen stool sample collected during the preceding 3 days to assess the persistence of the administered organisms in stool. Monitoring for adverse effects will also continue through Week 16 and any Week 12 lab abnormalities in safety lab tests will be followed up.

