- 10. Subjects who have received an experimental drug within 30 days prior to study entry
- 11. Subjects with known milk, peanut, tree nut, wheat, soy or shellfish allergies
- 12. Subjects who have been diagnosed with a sexually transmitted disease including, but not limited to, HIV, syphilis, herpes, gonorrhea, hepatitis A, hepatitis B, and hepatitis C
- 13. Hospitalization for any reason within the 3 months prior to study entry (Same day surgery center visits/procedures allowed)
- 14. Any active GI disease
- 15. History of any surgery on the gastrointestinal tract except appendectomy and cholecystectomy
- 16. Cystic fibrosis
- 17. Subjects with any condition that the investigator deems as a sound reason for disqualification from enrollment into the study

Whole Biome Study No: WB01-202_Ver 2_Amend 3
06/19/18

K. Removal of Subjects from Study Participation:

 Withdrawal of Consent - Subject wishes to withdraw from the study as outlined in the informed consent form. All subjects reserve the right to withdraw from the study without prejudice to themselves or their future medical care.

- 2. Adverse Event Subject experiences an adverse event, which in the investigator's opinion necessitates withdrawal from the study.
- 3. Investigator Decision Investigator assessment that it is in the subject's best interest to terminate participation.
- 4. Protocol Violation Includes subject non-compliance, documented pregnancy, study entry criteria violation, and/or initiation of an unacceptable concomitant medication, especially antibiotics, unless approved by Sponsor.
- 5. Lost to Follow-Up Subject fails to return for study visits and cannot be reached with reasonable attempts.
- 6. Administrative Reason Includes discontinuation of the study protocol by the sponsor, the Food and Drug Administration (FDA), or other regulatory authority, and/or discontinuation of the study site's participation in the study protocol.

Any withdrawal from the study will be fully documented. The documentation will include reasons for the withdrawal and details of any sequelae (followed through until the symptoms have resolved or returned to baseline levels) if the reason for withdrawal was an adverse event. Whenever possible, subjects terminating early will have the procedures outlined in Visit 7. (Note: If the subject has been receiving Study Product for <4 weeks, the MTT and inflammatory markers should be omitted.)

L. Subject Information and Samples:

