Once screened and qualified for entry, subjects will be instructed as follows:

- 1. Take no new prescription or over-the-counter medications excluded by the protocol without prior notification of the investigator.
- 2. Remain on their usual diet and exercise regimen throughout the study unless instructed to change by the investigator.
- 3. Fast overnight for at least 8 hours (no food or beverage except water) prior to each study visit except for the Screening Visit. (Note: This includes tea and coffee.)
- 4. Not donate blood for the duration of the study.

The sponsor should be contacted if the investigator is informed of any violations of these restrictions. The sponsor will decide whether a subject with restriction violations will be granted

Whole Biome Study No: WB01-202_Ver 2_Amend 3 06/19/18

Page 13 of 45

a deviation and allowed to continue study participation.

M. Study Food Product:

Study product will consist of coated capsules designed to pass through the stomach intact and disintegrate in the terminal portion of the small intestine. Subjects will be instructed to take 3 capsules of the food product within 30 minutes before each morning and evening meal, beginning with the evening meal on the day of randomization (Visit 1, Day 0) through the completion of Visit 7 (Week 12). The capsules will be identical in general appearance, size, and color across all the treatment arms. Each medical food study formulation capsule will contain the designated butyrate and barrier permeability-regulating commensal strains (Table 1); and consistent amounts of inulin, sucrose, trehalose, glycerin, hydroxypropyl methylcellulose, hydroxypropyl methylcellulose phthalate, titanium dioxide, polyvinylpyrrolidone, skim milk, and colloidal silicon dioxide. Placebo (WBF-0009) capsules will contain colloidal silicon dioxide. Commensal microbes are grown under GMP conditions using GRAS certified food grade reagents. All other ingredients are GRAS certified.

1. Packaging and Storage

The study food product will be provided in sealed, labelled screw cap bottles. Each bottle will contain 45 capsules to support 7 days of administration (42 capsules), plus 3 excess capsules to allow for replacement of lost capsules, etc. Additionally, the capsules for all treatment arms, including placebo (WBF-0009), will be identical in appearance to support the study blind.

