Three (3) capsules of study food product will be orally self-administered by the subject within 30 minutes prior to each morning and evening meal, as described above.

Study product dispositions and returns will be recorded on a sponsor-provided study product disposition form, to provide a complete accounting of the receipt, disposition, and return of each bottle of study product. As empty study product bottles are returned throughout the study, the bottles should be disposed of in an appropriate manner once the compliance assessment has been completed. At completion of Visit 7, the remaining unused study product will be returned to the sponsor or their designee.

Note: Due to packaging constraints (1 week supply with 3 extra capsules/bottle), the extra capsules should be utilized whenever possible to cover additional dosing to allow visit windows of -2 days to +2 days (+2 days only on Visit 7/week 12). Thus, subjects should be instructed to use all available capsules before opening a new bottle of study product. By capturing and utilizing these extra capsules, the vist windows for the study will be as follows (calculations based on defining the Baseline Visit as Day 0): Visit 2 (Day 12 to Day 15), Visit 3 (Day 26 to Day 30, Visit 4 (Day 38 to Day 42), Visit 5 (Day 54 to 58), Visit 6 (Week Day 68 to Day 72), Visit 7 (Day 82 to 86) and Visit 8 (Day 110 to Day 114)

N. Study Visits:

Prior to all study visits (screening visit excluded), subjects will be asked to fast overnight for at least 8 hours (i.e., no food or beverage except water). Subjects should report to the clinical study site in the morning of each scheduled visit (ideally between 0800 and 0900 hours). For all study visits, which require the subjects to be fasting, the subjects should refrain from administering the morning portion of study product prior to the visit, and bring the morning's

Whole Biome Study No: WB01-202_Ver 2_Amend 3 06/19/18

Page 15 of 45

portion of study product with them to the study-site to take in conjunction with their morning meal after the fasting blood work has been completed.

1. Screening Visit (Day-14 to Day -7)

The following items will be addressed during the Screening Visit:

- a. The informed consent and HIPAA authorization forms will be signed prior to performing any study procedures
- b. Review of inclusion/exclusion criteria to evaluate and confirm subject eligibility
- c. Complete medical history
- d. Collect vital signs, height, weight, and BMI

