
2. Adverse Events and Subject Withdrawals

Adverse Event

Any untoward medical occurrence associated with the use of a therapy in humans, whether considered treatment related or not treatment related.

Life-Threatening

Any untoward medical occurrence that places the patient or subject at immediate risk of death. It does not include an adverse event or suspected adverse reaction that, had it occurred in a more severe form, might have caused death.

Serious Adverse Event (SAE)

ANY SAE THAT OCCURS AFTER THE SIGNING OF THE ICF THROUGH 30 DAYS AFTER ADMINISTRATION OF THE LAST AMOUNT OF STUDY MEDICATION MUST BE REPORTED IMMEDIATELY (WITHIN 24 HOURS OF KNOWLEDGE) TO THE SPONSOR'S MEDICAL MONITOR [contact]). FAX THE SAE REPORT FORM TO THE NUMBER LISTED ON THE FORM.

An adverse event is considered "Serious" if, in the view of either the investigator or sponsor, it results in any of the following outcomes:

- Death
- A life-threatening adverse event
- Inpatient hospitalization or prolongation of existing hospitalization
- A persistent or significant incapacity or substantial disruption of the ability to conduct normal life functions

Whole Biome Study No: WB01-202_Ver 2_Amend 3 06/19/18

Page 22 of 45

A congenital anomaly/birth defect

Important medical events that may not result in death, be life-threatening, or require hospitalization may be considered serious when, based upon appropriate medical judgment, they may jeopardize the patient or subject and may require medical or surgical intervention to prevent one of the outcomes listed in this definition.

Any SAE, unexpected events, or death encountered during the study and for 30 days thereafter will be reported to the principal and/or co-investigators by the subject (immediately by telephone and subsequently in writing within five (5) days). The investigator will immediately report the SAE/unexpected event or death within 24 hours of being notified to the sponsor for review and assessment/causality confirmation, and to the IRB (per FDA requirements).

Unexpected Adverse Event

An adverse event is considered "unexpected" if it is not listed in the investigator brochure or is not listed at the specificity or severity that has been observed.

FDA guidelines recognize that:

- "Individual adverse event reports generally require an evaluation of their relevance and significance to the study, including an evaluation of other adverse events, before they can be considered an unanticipated problem," and

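### The last scheduled contact is nominally two days short of the 30-day SAE reporting period; separately, Visit 8 is timed from Day 0, so time off product varies by more than it need

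*Protocol*

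**What the plan says.** - **Visit timing.** The Note in Protocol Section M.4 states its windows with "calculations based on defining the Baseline Visit as Day 0" and ends the list with "Visit 7 (Day 82 to 86) and Visit 8 (Day 110 to Day 114". No text ties Visit 8 to the actual date of Visit 7 or of the last portion.
- **A competing statement in the same Note.** It also describes "visit windows of -2 days to +2 days (+2 days only on Visit 7/week 12", which can be read as allowing Visit 7 on Day 84 to 86 only. The listed window opens on Day 82.
- **End of product.** Section M has product taken "through the completion of Visit 7 (Week 12". Section F says: "Administration of study product will cease at the time of the 12-week visit as the subjects enter a 4-week wash-out period".
- **Purpose of Week 16.** Section D has the stool sample brought to this visit "to assess the persistence of the administered microorganisms in stool ~4 weeks after discontinuing ingestion", with fasting glucose, insulin and lipids drawn to look at persistence of change. The stool may be collected in the 3 days before the visit.
- **SAE period.** Section P.2 requires SAE reporting "THROUGH 30 DAYS AFTER ADMINISTRATION OF THE LAST AMOUNT OF STUDY MEDICATION". It also has subjects report SAEs, unexpected events and deaths to the investigator during the study and for a further 30 days.
- **Scheduled monitoring.** Section F takes adverse-effect monitoring to Week 16, and Appendix 1 schedules nothing later.
- **Early termination.** Section K: "Whenever possible, subjects terminating early will have the procedures outlined in Visit 7". Follow-up beyond that is described only for sequelae when an adverse event was the reason for withdrawal.

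**The concern.** The first issue is safety capture. The reporting period runs to day 30 after the last portion, but a subject who follows the schedule exactly is last seen on day 28, and one who stops early may not be contacted again after the termination visit. Adverse-event incidence is a primary endpoint (Section S), and two of the strains have not been given to humans before (Section C). An SAE in the last days of the period would reach the sponsor only if the subject, or someone on the subject's behalf, came forward.

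The second issue is the precision of the Week 16 measures. Persistence after stopping depends on time since stopping. If that time varies only because both visits are counted from baseline, the variation adds noise to detection of the strains and to the Week 16 changes in glucose, insulin and lipids, in a trial that expects about 20 completers per arm (Section H).

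**Working it through.** **Inputs.** Visit 7: Day 82 to 86, nominal Day 84 (Week 12). Visit 8: Day 110 to 114, nominal Day 112 (Week 16). Both are from Section M.4. The last portion is taken on the day of Visit 7 (Sections F and M). Stool is collected up to 3 days before Visit 8 (Section F). SAE period: 30 days after the last portion (Section P.2).

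**The plan's own figure.** Nominal time off product = 112 - 84 = 28 days. This reproduces the stated 4 weeks and is 30 - 28 = 2 days short of the SAE period.

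**Range under the listed windows.** Time off product = Visit 8 day - Visit 7 day.
- Minimum: 110 - 86 = 24 days.
- Maximum: 114 - 82 = 32 days.
- Spread for blood measures, which are drawn at the visit: 32 - 24 = 8 days.
- Earliest stool: 24 - 3 = 21 days. Latest: 32 days. Spread: 11 days.

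**If Visit 7 is limited to Day 84 to 86.** The maximum becomes 114 - 84 = 30 days. Blood is then 24 to 30 days and stool 21 to 30 days. The 24-day minimum is unchanged.

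**How often Visit 8 comes before day 30.** Counting every permitted pair of days:

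| Days off product | 24 | 25 | 26 | 27 | 28 | 29 | 30 | 31 | 32 |
|---|---|---|---|---|---|---|---|---|---|
| Listed windows (25 pairs) | 1 | 2 | 3 | 4 | 5 | 4 | 3 | 2 | 1 |
| Visit 7 on Day 84 to 86 (15 pairs) | 1 | 2 | 3 | 3 | 3 | 2 | 1 | 0 | 0 |

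- Listed windows: 1+2+3+4+5+4 = 19 of 25 pairs (76%) fall before day 30.
- Restricted Visit 7: 1+2+3+3+3+2 = 14 of 15 pairs (93%) fall before day 30.

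These are counts of permitted pairs. They become proportions of subjects only if all window days are equally likely, and the protocol gives no distribution of visit dates.

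**Sensitivity to the last portion.** If it is taken the evening before Visit 7, every interval is one day longer. The nominal interval is then 29 days, still short of 30, and the pairs before day 30 fall to 1+2+3+4+5 = 15 of 25.

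**Does re-anchoring Visit 8 fix both issues?** At 28 +/- 2 days from the last portion, blood measures span 26 to 30 days and stool spans 26 - 3 = 23 to 30 days. Visit 8 still comes before day 30 on 4 of the 5 window days (26, 27, 28, 29). Even a window centred on day 30 (28 to 32) leaves 2 of 5 days short. Re-anchoring therefore tightens the washout but does not close the SAE gap.

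**Early terminators.** Section H expects about 75 randomized and about 60 completing, so 75 - 60 = about 15 non-completers. This is a ceiling on the number without contact to day 30, because it includes subjects followed for an adverse event.

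**The case against.** The strongest reply is that nothing is contradicted. Section P.2 sets a reporting obligation and does not promise a visit on day 30. It also gives subjects a route to report late events, with onward reporting to the sponsor within 24 hours of the investigator being notified. For completers, at most the last 1 to 6 days of the period depend on that route. This stands: a reader might infer that the plan loses or excludes late SAEs, and it does not. What remains is that capture over those days is passive.

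A reader might also blame the SAE shortfall on the Day 0 anchor. That does not hold either. The shortfall arises because 28 is less than 30, and it is present when every visit is on its nominal day.

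On the washout, Section D says about 4 weeks, which accommodates a few days either way, and the windows apply equally to blinded, randomized arms. They bias no between-arm comparison. It would also be wrong to apply the 11-day spread to glucose, insulin and lipids. It belongs to stool alone and needs every extreme at once; blood varies by at most 8 days.

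Finally, the figure of about 15 non-completers invites the reading that all of them go unobserved after product. Some will have a termination visit that includes an adverse-event review, those who withdrew for an adverse event are followed for sequelae, and some will have withdrawn consent or been lost, so that no call could reach them. The documents support no estimate below that ceiling.

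**Conclusion.** Both points hold, separately and at modest size.

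1. **SAE capture.** The schedule, followed exactly, ends 2 days before the SAE reporting period does, and up to 6 days before it within the permitted windows. The nominal shortfall holds under either reading of the Visit 7 window, and with the last portion on the day of Visit 7 or the evening before. Early terminators have no scheduled contact after Visit 7 procedures unless an adverse event caused withdrawal. The weakness is reliance on passive reporting at the end of the period. Saying that most subjects fall short by window variation requires equally likely window days; the nominal 28 days does not.
2. **Washout spread.** Time off product is 24 to 32 days for blood and 21 to 32 days for stool (24 to 30 and 21 to 30 if Visit 7 is limited to Day 84 to 86). The effect is some added noise in secondary Week 16 measures, without bias between arms and without effect on the Week 12 glucose AUC or CRP endpoints.

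The first point carries more weight because it bears on safety observation in a trial with two first-in-human strains.

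**What to change.** - **SAE capture.** Add one AE/SAE phone contact at or after 30 days from the last portion for all reachable subjects, including early terminators, using the existing Week 6 and Week 10 phone-visit format. Cost: one extra short call per subject, with no added samples or clinic visits.
- **Visit 8 timing.** Time Visit 8 from the recorded date of the last portion, at 28 +/- 2 days. This narrows blood measures to 26 to 30 days and stool to 23 to 30 days. Cost: amendment wording, and one date field if the eCRF, which is not at hand, does not already hold it. Sites would book Visit 8 once the last-portion date is known.
- **Visit 7 window.** Reconcile the two statements in the Section M.4 Note, the listed Day 82 to 86 and the parenthesis about +2 days only, so that sites work to one window.

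The first two changes do different jobs, and neither replaces the other.

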- 4. Disposable Gloves 2 pairs
- 5. Sanitary Wipes
- 6. Ballpoint Pen

Figure 1: Stool Collection Device

When you get home, please place the cooler (containing the Stool Collection Bucket) into your freezer.

When you are ready to collect your stool sample, take the following actions in the order listed:

- 1. Completely empty bladder.
- 2. Remove all items from your kit bag and remove the Stool Collection Bucket from the cooler (leave the cooler itself in the freezer) and the transparent bag
- 3. Use a sanitary wipe to cleanse toilet seat and rim of toilet bowl.
- 4. Fill out the date (month/day/year) and check the box corresponding to the time of day on the bucket lid label with the provided ballpoint pen.
- 5. Remove the lid from the bucket and place the lid inside of the transparent bag.
- 6. Assemble the SCD by inserting the Collection Bucket (Figure 1B above) securely into the Stability Frame (Figure 1A above), as shown in Figure 2.

Note: Do not touch the inside of the bucket.

Figure 2: Assembled Stool Collection Device (SCD)

7. Lift the toilet seat and place the SCD horizontally on the edges of the toilet bowl. The narrow side of the frame should face towards the rear end of the toilet bowl (Figure 3A).

Note: Depending on your personal anatomy, repositioning the narrow side of the frame to face the front of the toilet bowl (Figure 3B) may better facilitate acquisition of stool sample.

Figure 3A

Figure 3B

8. Lower the toilet seat to secure the SCD (Figure 4A/Figure 4B).

Figure 4A

Figure 4B

Whole Biome Study No: WB01-202_Ver 2_Amend 3 06/19/18

Page 36 of 45

9. Sit on the toilet and arrange yourself so that the stool sample will fall directly into the bucket.

Note: Do not urinate or place toilet paper into the Collection Bucket.

- 10. When finished, use toilet paper to clean yourself and discard used toilet paper outside of the bucket.
- 11. Flush the toilet.
- 12. Then, lift the toilet seat and remove the SCD from the toilet.
- 13. Set the SCD on a flat surface.
- 14. Push down on the Stability Frame to detach it from the Collection Bucket.
- 15. Discard frame.
- 16. Remove the lid from the transparent bag and push the lid onto the Collection Bucket (Figure 5). The lid is secure when a "snap" is heard.
- 17. Place the sealed Collection Bucket into the empty transparent bag and close the bag.
- 18. Place the closed transparent bag with collected stool sample into the cooler.
- 19. Store the cooler in the freezer and leave in the freezer until your next clinic visit.
- 20. At your next clinic visit, bring your cooler (with sample inside) and give to the clinical coordinator.

Figure 5

THANK YOU FOR YOUR PARTICIPATION IN THIS IMPORTANT STUDY!

Whole Biome Study No: WB01-202_Ver 2_Amend 3 06/19/18

Page 37 of 45

Appendix 3

Meal Tolerance Test

Overview

A meal tolerance test (MTT) is analogous to the traditional glucose tolerance test. Instead of a large glucose challenge, which is unphysiologic, the MTT employs a standardized mixed meal. In the WB01-202 study, we are using Boost Plus® as the challenge (Caloric content = 720 calories; 50% carbohydrate, 16% protein and 36% fat). Blood samples are taken fasting and at set times from the start of the meal to measure plasma glucose and insulin.

Procedure

- 1. The subject should not have anything to eat or drink, except for water and the Boost Plus® meal, until the MTT test has been completed.
- For convenience and comfort of the subject, placement of an indwelling venous sampling device to limit the number of needle sticks required to obtain the blood samples is recommended.
- 3. Following the instructions regarding which blood tubes to use, included in the self-contained glucose tolerance test (GTT) kit provided by Quest Laboratories, draw the fasting glucose and insulin samples (~5mL of blood): Note: Any other fasting blood samples scheduled for the visit should also be drawn prior to the subject beginning to drink the Boost Plus® liquid meal.
- **4.** Provide the subject with 16 ounces of Boost Plus® (two 8-ounce containers) to drink over 15 minutes.
- 5. Record the clock time when the subject begins to drink the Boost meal and start a timer to track the time of the subsequent blood samples.
- 6. Record the time the subject completes ingestion of the Boost challenge.
- 7. At 30, 60, 90, 120 and 180 minutes following the start of the meal, draw a sample for plasma glucose and insulin following the instructions accompanying the GTT kit as to which blood tubes to use for the samples. Note: If an indwelling venous sampling device is being used, remember to draw and discard an adequate of blood to remove the solution used to keep the device patent between blood draws so that the samples taken are not diluted.
- **8.** After the sample has been taken, if an indwelling sampling device is being used, remember to take the measures needed to maintain patency of the device until the time for the next sample.
- **9.** Record the clock time the sample was drawn.
- **10.** When the 180-minute sample has been obtained, remove the sampling device, if used. The subject can now have anything they would like to eat or drink

Whole Biome Study No: WB01-202_Ver 2_Amend 3 06/19/18

Page 38 of 45

Appendix 4

Hospital Anxiety and Depression Scale (HADS)

Hospital Anxiety and Depression Scale (HADS)

Tick the box beside the reply that is closest to how you have been feeling in the past week.

Don't take too long over you replies: your immediate is best.

D	A	Don't take too long over you	D	A	
_		I feel tense or 'wound up':			I feel as if I am slowed down:
	3	Most of the time	3		Nearly all the time
	2	A lot of the time	2	*	Very often
	1	From time to time, occasionally	1	0	Sometimes
_	0	Not at all	0		Not at all
-	-	1101 01 01	-	*	
		I still enjoy the things I used to enjoy:			I get a sort of frightened feeling like 'butterflies' in the stomach:
0		Definitely as much)	0	Not at all
1		Not quite so much	ŝ	1	Occasionally
2		Only a little		2	Quite Often
3		Hardly at all		3	Very Often

	2	I get a sort of frightened feeling as if something awful is about to happen:		(A)	I have lost interest in my appearance:
	3	Very definitely and quite badly	3	16	Definitely
	2	Yes, but not too badly	2	ii -	I don't take as much care as I should
	1	A little, but it doesn't worry me	1		I may not take quite as much care
	0	Not at all	0		I take just as much care as ever
		I can laugh and see the funny side of things:			I feel restless as I have to be on the move:
0		As much as I always could		3	Very much indeed
1		Not quite so much now)	2	Quite a lot
2		Definitely not so much now		1	Not very much
3		Not at all	8	0	Not at all
		Worrying thoughts go through my mind:			I look forward with enjoyment to things:
	3	A great deal of the time	0		As much as I ever did
	2	A lot of the time	1		Rather less than I used to
	1	From time to time, but not too often	2	Ĩ	Definitely less than I used to
	0	Only occasionally	3	Ÿ	Hardly at all
_	-		6		
_		I feel cheerful:			I get sudden feelings of panic:
3		Not at all	Ų.	3	Very often indeed
2		Not often		2	Quite often
1		Sometimes		1	Not very often
0		Most of the time		0	Not at all
		I can sit at ease and feel relaxed:			I can enjoy a good book or radio or TV program:
=	0	Definitely	0	Š.	Often
	1	Usually	1		Sometimes
	2	Not Often	2		Not often
_	3	Not at all	3		Very seldom

Please check you have answered all the questions

Scorin	ng:		
Total	score: Depression (D)	Anxiety (A)	
0-7	= Normal		
8-10	= Borderline abnormal (border	line case)	
11-21	= Abnormal (case)		

Whole Biome Study No: WB01-202_Ver 2_Amend 3 06/19/18

Page 40 of 45

Appendix 5

WB01-202 Subject Optional Questionnaire FACIT-D & AD (V.4) & Victoria Bowel Performance Scale (BPS)

Please look at the Victoria Bowel Performance Scale below and circle the BPS (e.g. -2) that most closely resembles your bowel movements.

				Victoria B	owel Perforr	nance Scale			
Constipation					Normal			Diarrhea	
Visit 7/Week 12 (last day of treatment)	-4	-3	-2	-1	G	+1	+2	+3	+4
Visit 8/Week 16 (4 weeks after treatment)	-4	-3	-2	-1	G	+1	+2	+3	+4

CTORIA DSPICE										
- 4	- 3	- 2	-1	BPS Score G	+1	+ 2	+ 3	+4		
		Constipation		Normal		Diarrhea	_			
Impacted or Obstructed +/- small leakage	Formed Hard with pellets	Formed Hard	Formed Solid	Characteristics Formed Semi-solid	Formed Soft	Unformed Loose or paste-like	Unformed Liquid ±mucous	Unformed Liquid ±mucous		
No stool produced after Goal plus 3 days	Goal plus 3 or more days delay	Goal plus 1-2 days delay	Patient's Goal frequency occurs	Pattern Patient's Goal for frequency	Patient's Goal frequency occurs	Goal or more frequent than goal	More frequent than goal	More frequent than goal		
Unable to defecate despite maximum effort or straining	Major effort or straining required to defecate	Moderate effort or straining required to defecate	Minimal or no effort required to defecate	Control Minimal or no effort to defecate	Minimal or no effort required to control urgency	Moderate effort required to control urgency	Very difficult to control urgency and may be explosive	Incontinent or explosive; unable to control or unaware		

Instructions for Use

- BPS is a 9-point scale. It is a single score, based on the overall 'best vertical fit' among the above three parameters [characteristics, pattern, control] and is recorded for example as: BPS +1, BPS -3 or
- Look vertically down each BPS level to become familiar with how the three parameters of characteristics, pattern & control change in gradation from constipation to diarrhea
- Look vertically down each BYS level to become annihilar with now the three parameters of characteristics, pattern a control change in gradation from constipation to diarrhea.
 For the bowel pattern, it is the patient's goal that is the determining factor. The goal is recorded in the center section, marked with the patient's desired goal for how often they would prefer to have a bowel movement. Based on their goal, then the actual frequency is either within that goal, delayed beyond the goal, or more frequent than the goal. If the goal is met, the score is BPS G.
 Patients may use different words than above to describe their bowel activity. One must use clinical judgment in deciding which boxes are most appropriate.
 For patients with ostomies or short bowel syndrome, all 3 parameters should be assessed according to closeness to the patient's desired goal.
 In potential confounding cases, determination of the most appropriate BPS score is made using the following methods:

- Two vertically similar parameters generally outweigh the third;
 Indicate the single priority weighting among parameters is Characteristics > Pattern > Control of the single priority weighting among parameters is Characteristics > Pattern > Control of the single priority weighting among parameters is Characteristics > Pattern > Control of the single priority weighting among parameters is Characteristics > Pattern > Control of the single priority weighting among parameters is Characteristics > Pattern > Control of the single priority weighting among parameters is Characteristics > Pattern > Control of the single priority weighting among parameters is Characteristics > Pattern > Control of the single priority weighting among parameters is Characteristics > Pattern > Control of the single priority weighting among parameters is Characteristics > Pattern > Control of the single priority weighting among parameters is Characteristics > Pattern > Control of the single priority weighting among parameters is Characteristics > Pattern > Control of the single priority weighting among parameters is Characteristics > Pattern > Control of the single priority weighting among parameters is characteristics > Control of the single priority weighting among parameters is characteristics > Control of the single priority weighting among parameters is characteristics > Control of the single priority weighting among parameters and the
- When recording BPS in hospital or facility patient charts where charting is required every shift or daily, a BPS 'X' is used to indicate no bowel assessment was done in that timeframe. Otherwise, the actual BPS number is recorded. Do not write "0" as it is misleading; the correct recording would be BPS X.
- The BPS cannot be applied when there is no expected functioning bowel, as may occur with patients on TPN or if imminently dying with no oral intake. If this is the case, the correct recording is BPS

The Victoria Bowel Performance Scale (BPS), originally published in the Journal of Pain & Symptom Management 2007, has been slightly revised to incorporate the patients' goal for bowel pattern. Downing, Hawley, Barwich and Black, 2009. © Victoria Hospice Society, 2016. For permissions, please send request via email to [contact]

Subject Initials ____ Subject No. ____ Visit 7 / Visit 8 (circle one) Date / /

Whole Biome Study No: WB01-202_Ver 2_Amend 3 06/19/18

Page 41 of 45

WB01-202 Subject Optional Questionnaire FACIT-D & AD (V.4) & Victoria Bowel Performance Scale (BPS)

Please circle or mark one number per line to indicate your response as it applies to the past 7 days.

PHYSICAL WELL-BEING	Not at all	A little bit	Some- what	Quitea bit	Very much
I have a lack of energy	0	1	2	3	4
I have nausea	0	1	2	3	4
Because of my physical condition, I have trouble meeting the needs of my family	0	1	2	3	4
I have pain	0	1	2	3	4
I am bothered by side effects of treatment	0	1	2	3	4
I feel ill	0	1	2	3	4
I am forced to spend time in bed	0	1	2	3	4
SOCIAL/FAMILY WELL-BEING	Not at all	A little bit	Some- what	Quitea bit	Very much
I feel close to my friends	0	1	2	3	4
I get emotional support from my family	0	1	2	3	4
I get support from my friends	0	1	2	3	4
My family has accepted my illness	0	1	2	3	4
I am satisfied with family communication about my illness	0	1	2	3	4
I feel close to my partner (or the person who is my main support)	0	1	2	3	4
Regardless of your current level of sexual activity, please answer the following question. If you prefer not to answer it, please mark this box and go to the next section.					
I am satisfied with my sex life	0	1	2	3	4
Initials Subject No Visit 7 / Vi	sit 8 (circ	le one)	Date/	_/_	

Whole Biome Study No: WB01-202_Ver 2_Amend 3 06/19/18

Page 42 of 45

WB01-202 Subject Optional Questionnaire FACIT-D & AD (V.4) & Victoria Bowel Performance Scale (BPS)

